Neurocognitive impairment may be both an important contributor to, as well as a result of, alcohol use and TBI. AUD is associated with, or causal to, a wide variety of neurobehavioral harms. These include impulsivity, risk-taking behavior, irritability/mood instability, depression, and suicide risk. HHAU is also associated with deficits in executive functioning, learning, memory, and decision making, with increased impulsivity and risk-taking. Both HHAU's and TBI's association with impairments in self-control and decision-making are linked to ventromedial and orbitofrontal cortex dysfunction. Thus, both TBI and HHAU may independently and additively alter cognitive, emotional, and behavioral functioning. These alcohol- and TBI-related impairments can also synergistically increase the potential for risk-taking and contribute to many of the harmful behaviors seen in veterans with HHAU and TBI. By extension, they also affect their families, and the community at large.

NAC has been proposed as a neuroprotective agent that may benefit TBI, mediated through antioxidant and anti-inflammatory effects⁷ and it may assist in reducing alcohol use. Reducing alcohol use and improving brain injury symptoms via NAC treatment may have the potential to improve cognitive functioning and reduce risky behavior in veterans with TBI. Reducing impulsivity and risk-taking propensity can be expected to reduce harmful behaviors that are tied to poor adherence to medical care, marital relationship problems, domestic and other forms of violence, and suicide. If, as expected, NAC treatment improves the management of TBI and AUD, it would have unambiguous benefits both for active duty military personnel and veterans.

Improving the care of veterans with TBI and unhealthy alcohol use is likely to help families and communities affected by the sequelae of these problems. Moreover, treatments that help veterans with TBI and unhealthy alcohol use are likely to be applicable to the general population of individuals with these comorbid problems.

The objectives of the study are: (a) to successfully recruit 30 veterans with mild TBI and hazardous or harmful alcohol use; (b) to test primary and exploratory hypotheses as described below.

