Outcomes, products and deliverables: Outcomes: The primary treatment outcome will be percent heavy drinking days of alcohol per week. The secondary outcome will be TBI symptom severity as measured by the Neurobehavioral Symptom Inventory (NSI). The exploratory outcomes will be levels of executive functioning (impulsivity, risk-taking, and decision making) and other neurocognitive domains assessed over the course of the study. *Products:* Data will be collected on 8 weeks of treatment plus week 12 follow-up. *Deliverables:*

This study is being sponsored by the Department of Defense (DOD) Telemedicine and Advanced Technology Research Center (TATRC).

II. RESEARCH PLAN

A. GOALS AND SPECIFIC AIMS

The overall goal of the project is to improve the care of veterans with traumatic brain injury and unhealthy alcohol use. We will conduct a pilot controlled clinical trial to assess the efficacy of N-acetylcysteine (NAC) to reduce alcohol use and improve brain injury symptoms in veterans with TBI who consume alcohol at *hazardous or harmful* levels. This project builds upon our current ITN-funded research on topiramate pharmacotherapy for unhealthy alcohol use in veterans with TBI.

A.1. PRIMARY AIMS:

Aims:

Measure both alcohol use and TBI symptom severity over the course of the 12-week study in order to detect differential efficacy of NAC and placebo. Alcohol use treatment outcome will be the Percent Days of Heavy Drinking (PHDD) of alcohol

A heavy drinking day is defined using NIAAA (2007) criteria: any day with 5 or more drinks per day for men or 4 or more drinks per day for women⁸. The choice of PHDD as the primary outcome is based on its endorsement by a recent NIAAA consensus conference⁹ and its increasing use in clinical trials ¹⁰⁻¹². TBI symptom severity will be measured with the Neurobehavioral Symptoms Inventory (NSI)^{13,14} a measure of postconcussive symptom severity.

Hypotheses:

Our **two primary** aims examine group differences, to detect differential efficacy of NAC vs placebo (*between-group analyses*). We will test the following hypotheses with between-groups analyses:

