Review Medical Event Monitoring System (MEMS)	
Drug Accountability	
Dispense Medication	

D.5.c. Follow-up Phase

FOLLOW-UP PHASE The last visit, or follow-up, will take place on week 12. This visit will last between 3 and 3.5 hours.

FI. [name]
Measures
Concurrent Medications Form
Concurrent Treatments Form
AE Spontaneous Form
AE Checklist Form
TLFB – Timeline Followback
Demographics
CIWA – Clinical Institute Withdrawal Assessment for Alcohol, DSM-IV Version (CIWA-AD)
NSI – Neurobehavioral Symptom Inventory
AUDIT – Alcohol Use Disorders Identification Test
SIP-2R – Short Index of Problems
OCDS – Obsessive Compulsive Drinking Scales
PACS – Penn Alcohol Craving Scale
SHAS – Subjective High Assessment Scale
EVAR-B – Evaluation of Risks Scale
PCL – PTSD Checklist
POMS – Profile of Mood States
BDI-II – Beck Depression Inventory
BAI – Beck Anxiety Inventory
BIS-11 – Barrett Impulsivity Scale
PSQI – Pittsburgh Sleep Quality Index
ISI – Insomnia Severity Index
DERS – Difficulties in Emotion Regulation Scale
DTS – Distress Tolerance Scale
APT – Alcohol Purchase Task
WTAR - Wechsler Test of Adult Reading
HVLT-R – Hopkins Verbal Learning Test
TMT A + B – Trail Making Test A & B
WAIS 4 – Arithmetic
WAIS 4 – Antimetic WAIS 4 – Digit Span
Stroop Inhibition
COWA – Controlled Oral Word Association
BART – Balloon Analogue Risk Task
IGT – Iowa Gambling Task
SST – Stop Signal Task
AAT – Alcohol Approach Task
End of Study Completion Questionnaire
Procedures
Breath Alcohol Concentration (BrAC)
Clinical Labs – renal panel, hepatic panel and GGT
Ethyl Glucuronide (EtG)
Urine Drug Screen
Phosphatidylethanol (PEth)
Vitals (Blood pressure, heart rate, temperature)
Weight
Assess birth control method and perform urine pregnancy test (women only)
Drug Accountability
Dispense Medication

D.6. DATA ANALYSIS

The proposed study has primary, secondary, and exploratory outcomes.

D.6.a. Primary Outcome Measure

PI: [name] The primary outcome measure will be the change in number of drinking days from baseline to end of study, associated with NAC treatment.

1) Primary Hypothesis

The *Primary* hypotheses are that NAC treatment will be more efficacious than placebo in reducing PHDDs and TBI symptom severity (NSI).

2) Data Analytic Technique for the Primary Outcome

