Percent Heavy Drinking Days (PHDD): Negative binomial regression accommodates over dispersion and derives as an alternative to Poisson regression (most natural for analyzing count data). Heavy percent drinking days is often over-dispersed, positively skewed count data. Therefore, we will use random-intercept zero-inflated negative binomial model, modeling week (week 1 - week 8) as a continuous variable to analyze group differences in PHDD. *Neurobehavioral Symptom Inventory (NSI):* We will use random-intercept linear mixed models to explore the efficacy for NAC related reduction in TBI symptom severity measured by the NSI. Time period will be treated as a repeated effect, with correlations between time periods within participants modeled by an unstructured correlation matrix where appropriate. Model assumptions will be tested and required modifications will be performed. Both models will included fixed effect for week, treatment group (NAC and placebo), and the interaction between treatment group and week. Baseline alcohol consumption and NSI means will be used as respective covariates in group comparisons to control for pre-study and study enrollment effects.

3) Power Analyses for the Primary Outcome

We conducted a power analysis on our current pilot study of topiramate treatment of *alcohol dependence* in veterans with PTSD (see Section C.2.b.). For the outcome measure of percent drinking days (PDD), the effect size from the pilot data comparing week 12 to baseline within the topiramate group is d = 1.87. Because the proposed project is focused on veterans with TBI who have *hazardous* as well as harmful alcohol use, rather than just harmful use (alcohol dependence), we assume that the participants may start at a lower baseline level of DD in the proposed study than in the pilot study. This may not allow us to show as much improvement in the proposed study as in the completed pilot study of PTSD and alcohol dependence. Therefore, it would seem reasonable to target an effect size approximately half of what we found in our pilot study, i.e. d=0.9. A sample size of 16 for the topiramate arm of our proposed placebo-controlled pilot will allow us to detect a within-subjects effect size of d = 0.9, with 80% power at alpha = .05.

D.6.b. Exploratory outcomes/exploratory hypotheses

1) Exploratory Hypotheses

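### The power section for the primary outcome (D.6.a, item 3) sizes a pre-post change in a topiramate arm, not NAC versus placebo on PHDD, and its 80% cannot be reproduced from the inputs it states

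*Combined protocol and SAP*

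**What the plan says.** D.6.a, item 3, starts from an earlier topiramate pilot in veterans with PTSD and alcohol dependence. Its outcome is percent drinking days, and its effect size, "comparing week 12 to baseline within the topiramate group is d = 1.87", is a change within one arm. The section expects lower baseline drinking in the new trial, halves the figure to about 0.9, and concludes: "A sample size of 16 for the topiramate arm of our proposed placebo-controlled pilot will allow us to detect a within-subjects effect size". The power claimed for the halved effect is 80%, at a .05 level. The section does not give the sidedness of the test, the standardiser of d, the pre-post correlation or an allowance for dropout.

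The rest of the plan describes something else:
- **Comparison.** The two primary "aims examine group differences, to detect differential efficacy of NAC vs placebo" (A.1). Item 1 of D.6.a agrees: the "hypotheses are that NAC treatment will be more efficacious than placebo in reducing PHDDs" and NSI score.
- **Size.** The objective is "to successfully recruit 30 veterans with mild TBI and hazardous or harmful alcohol use" (Synopsis). Allocation is 1:1 (D.3.f), so 15 per arm.
- **Model.** PHDD over weeks 1 to 8 goes into a random-intercept zero-inflated negative binomial model with a baseline covariate (D.3.i and D.6.a, item 2).
- **Primary outcome.** The opening sentence of D.6.a instead names the change in number of drinking days from baseline to end of study.
- **Other power statement.** D.3.i says that n = 30 gives power .80 for an effect of about .65, one-tailed at alpha .05, without naming an outcome.

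**The concern.** A power statement should describe the test that will be run. This one differs from the planned test in drug, contrast, outcome and arm size. Its week-12 time point also falls four weeks after treatment ends and outside the weeks in the PHDD model.

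Contrast matters most. A change within a treated arm includes response to counselling, placebo response and regression to the mean, all of which the placebo arm shares. Half of such a change is not an estimate of NAC minus placebo. The reason given for halving does not fit either: it assumes that hazardous drinkers without a disorder will enrol, yet inclusion criterion 4 requires moderate or severe alcohol use disorder of everyone.

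The protocol says it assesses efficacy and will yield an effect estimate for planning a larger trial. If readers believe the trial has 80% power at d = 0.9 or at .65, they may read a null result as evidence against NAC when the trial was unlikely to detect anything but a very large effect.

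**Working it through.** **1. Reproducing the stated 80%.** Inputs from D.6.a, item 3: n = 16, d = 0.9, alpha .05, within-subjects. For a paired t-test with d on the SD of the differences, the noncentrality is d√n = 0.9 × 4 = 3.6 with 15 df. By the noncentral t distribution:
- two-sided power 92%; one-sided 96%;
- 80% two-sided is reached at d = 0.75 with n = 16, or at n = 12 with d = 0.9 (81%).

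Neither sidedness gives 80%.

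**2. What would give about 80%.** If d is on the raw SD, then dz = d / √(2(1 − r)), with r the pre-post correlation:

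| r | dz | Power, two-sided |
|---|---|---|
| 0 | 0.64 | 66% |
| 0.28 | 0.9/√1.44 = 0.75 | 80% |
| 0.5 | 0.90 | 92% |
| 0.7 | 1.16 | 99% |

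Other routes are 12 evaluable of 16 (81%), or alpha .05/3 two-sided (80.4%). With the 81% completion quoted from the earlier trial, 16 × 0.81 ≈ 13 remain and power is 84.5%. The section states none of these assumptions.

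**3. The comparison the trial will make.** Two-sample t-test, 15 per arm, unadjusted, no dropout; noncentrality d√(15/2), 28 df, alpha .05:

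| Quantity | One-sided | Two-sided |
|---|---|---|
| Power at d = 0.9 (noncentrality 0.9 × 2.739 = 2.46) | 78% | 66% |
| Power at d = 0.65 (noncentrality 0.65 × 2.739 = 1.78) | 54% | 40% |
| d detectable with 80% power | 0.93 | 1.06 |

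The .65 sentence in D.3.i therefore does not fill the gap. One-sided, .65 would need about 30 per arm.

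**4. Scale in heavy drinking days.** Table 2 (C.5) gives heavy drinking days per week as 4.8 (SD 1.9) with TBI and 4.8 (SD 2.4) without. These are 90-day baseline averages from an earlier AUD/PTSD sample, so using either SD here is an assumption:
- SD 1.9: 0.93 × 1.9 = 1.8 days/week one-sided; 1.06 × 1.9 = 2.0 two-sided.
- SD 2.4: 0.93 × 2.4 = 2.2 one-sided; 1.06 × 2.4 = 2.5 two-sided.

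Against a mean of 4.8, this is a difference of roughly 1.8 to 2.5 heavy days a week.

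**The case against.** **The t-test is not the planned analysis.** This stands. A baseline covariate could raise power: as an ANCOVA approximation with an assumed baseline correlation of 0.3, 0.5 or 0.7 (none is in the documents), d = 0.9 at 15 per arm has 70%, 78% or 91% power two-sided. Repeated weeks could also help. The modified Bonferroni adjustment in D.3.i works the other way. The figures above are therefore approximations, and on the one-tailed basis that D.3.i states, the shortfall at d = 0.9 is only two points.

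**Outcome and time point are not wholly foreign.** Drinking days at week 12 fit the opening sentence of D.6.a. That is fair, but the sentence itself conflicts with the hypothesis and model that follow it, so it needs reconciling too.

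**The text says within-subjects, and this is a pilot sized by funding.** Both are true. A careful reader would not take 0.9 as between-group, and the paragraph does not set the sample size. That reader is still left with no valid power figure for the primary comparison.

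**Stronger readings the documents do not support.** A reader might infer that 80% is simply an arithmetic error. With sidedness, standardiser, correlation and dropout all unstated, only non-reproducibility can be shown; on the plain paired reading, 80% understates power. A reader might also notice that a one-sided two-sample test with 16 per arm detects d = 0.90, and a one-sided paired test with 16 detects 0.65, and conclude that the number was mislabelled or the two effect sizes swapped. But the .65 sentence says n = 30, a one-tailed paired test with 15 gives 77% at .65, and .65 equally matches 30 per arm. The origin of the figures cannot be settled from the text.

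**Conclusion.** The point holds. D.6.a, item 3, gives no power for NAC versus placebo on PHDD, and neither d = 1.87 nor d = 0.9 has any basis as a between-group effect. This does not depend on any calculation. Secondarily, the stated 80% cannot be reproduced from the stated inputs.

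At 15 per arm the trial can detect, with 80% power, a standardised difference of about 0.93 one-sided or 1.06 two-sided. This assumes an unadjusted two-sample t-test, full retention and alpha .05 without multiplicity adjustment. The planned model may do somewhat better or worse; the documents give no basis for saying by how much. The difference between 16 and 15 is minor by itself: it moves the two-sided paired figure from 92% to 90%.

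**What to change.** - Delete the topiramate paragraph in D.6.a, item 3, with its d = 1.87 and d = 0.9 targets.
- Put in its place one statement for NAC versus placebo on PHDD at 15 per arm, giving alpha after any multiplicity adjustment, sidedness, detectable effect and method, and labelled as an approximation to the planned mixed model.
- If the effect is converted to heavy days per week, say that the Table 2 SD of 1.9 is an assumed baseline value from an earlier AUD/PTSD sample with TBI, and show a range.
- Reconcile this statement with the .65 sentence in D.3.i, so that the plan contains one power claim, and with the opening sentence of D.6.a, so that it names one primary drinking outcome.
- State that the pilot is not powered for smaller effects.

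The cost is a wording amendment. Sample size, conduct and planned model are unchanged, but the stated power becomes less favourable.

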Random assignment will be followed by 8 weeks of treatment with NAC or placebo. Study medications will be identical in appearance. Participants will be provided with 10 days of medication at each weekly visit to increase the likelihood of medication continuity in case of a missed visit. Extra medication will be collected from participants at each visit. Study medication (NAC or placebo) will be started at a dose of 600 mg bid (1200 mg per day), for 3 days, then 1200 mg bid for 4 days, (2400 mg per day), then 1800 mg bid (3600 mg per day) for weeks 2 through 8. Similar doses have been shown to be an effective dose in other addiction studies (see A.2.). If the participant experiences significant side effects during the titration period, the dosage may be adjusted as necessary. Patients will be treated with the highest dose tolerated, not to exceed a total of 3600 mg per day, but may be reduced by 600mg increments as needed. Wellspring Compounding Pharmacy, a compounding Pharmacy – a compounding pharmacy recommended by the University of California, San Francisco School of Medicine Pharmacy -- will supply NAC study capsules and matching placebo capsules. The policies and procedures concerning good compounding practices and environmental, instrumental and procedural quality assurance have been approved by the California State Board of Pharmacy. The SFVAMC Research Pharmacist will directly receive all study medications from Wellspring Compounding Pharmacy and store in appropriate environmental conditions. The dosage is to be determined by a study physician at each weekly visit, using the titration schedule as a guide. An official VA prescription form must be filled out by a study physician for each patient at each visit. A research associate will pick up the prescription from the SFVAMC pharmacy. The date, time and amount of study compound dispensed will also be recorded in the subject's electronic medical file. Participants are instructed to return all unused study medication weekly. The number of returned capsules will be documented.

D.3.h. Medical Management

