Estimates of NAC vs placebo for a larger study of HHAU and TBI.

We plan to derive a reliable estimate of effect for planning a large RCT from this small controlled pilot study. It will be useful to obtain estimates of variability in order to inform future controlled trials of NAC treatment for alcohol use. Our sample of n=30, with power of .80 will have the ability to detect an effect size of approximately .65 (one-tailed, alpha = .05). This is conventionally considered a medium effect size. To test for efficacy, we plan to implement intent-to-treat analyses, therefore including all participants randomized to trial. To examine estimates of harm, we will complete Per-Protocol analyses using data from participants exposed to study medications.

Study Limitations/Potential Problems.

Veterans Alcohol TBI PI: [name]

Recruitment, retention, missing data, and safety issues have been the most difficult hurdles facing clinical trials in AUDs. We believe that our research team is demonstrating a high level of success in recruiting (See Table 5) and retaining similar participants with TBI and HHAU, with 81% of participants completing the PI's pilot trial of TOP, a medication with a much higher adverse event profile¹²⁹. Similarly, there has been little missing data, with 81% of weekly study visits attended. Moreover, the use of a mixed-effects model allows for all available data in model estimation. Finally, human participant safety, although a prime concern, is relatively low in the use of NAC¹⁷⁰ (See Human Subjects Section)

I I. Da	[name]			
Table 5. Pl's current trial of				
topiramate in HHAU and mTBI				
Prescreened 255				
Screened (Signed Consent)	25			
Randomized	17 (53%)			
Percent Visits Attended	80.88%			
Percent Attended Week 12	81.25%			

D.3.j. Phlebotomy and Urine Drug Testing

Phlebotomy will be performed at screening, week 4, 8, and 12. Urine drug testing will be performed at screening, week 4, week 8, and week 12.

D.3.k. Participant Payment

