PI: [name] This form is to be administered upon completion of the study (as defined by attending Week 12 visit) or at termination to document the last day of study medication ingestion, number of visits attended and/or reasons for terminating.

D.4.b.7. PARTICIPANT - END-OF-STUDY QUESTIONNAIRE

This measure is administered at Week 12 to assess the participant's opinion of participation and what was helpful/useful during treatment.

D.4.c. Measures of Health/Biological Safety

D.4.c.1. OVERVIEW OF HEALTH/BIOLOGICAL SAFETY MEAUSURES

Safety evaluations will include: entry medical history and physical examination, weekly vital signs monitoring, weekly breath alcohol concentration (BrAC), weekly CIWA-AD (clinical alcohol withdrawal assessment), weekly monitoring for adverse events, suicide risk assessment at baseline, periodic clinical laboratory tests (complete labs including urinalysis at baseline, periodic renal function and liver function tests, and urine pregnancy tests performed every 28 days on women of childbearing potential.

D.4.c.2. MEDICAL HISTORY AND PHYSICAL EXAMINATION

A medical history and physical examination will be completed at baseline during the screening period. Study physicians will screen medical records. This information will be recorded on the physical examination form.

D.4.c.3. CLINICAL LABORATORY TESTS FOR HEALTH AND SAFETY MONITORING

The following tests will be performed by the San Francisco VAMC clinical laboratory.

Clinical laboratory tests at baseline (Screening phase):

Blood samples will be collected for serum chemistry, liver panel (LFTs), renal panel and complete blood count (CBC) and a urine sample will be collected for urinalysis, and, for women – urine pregnancy test.

If AST or ALT are >5 times the upper limit of the normal range, or if serum bilirubin is >2 times the upper limit of normal, these tests will be repeated, and if the repeat tests still exceed these limits, the participant will be excluded.

Clinical laboratory tests for health and safety monitoring throughout the study: Renal and hepatic panels will be repeated at Visits 4 and 8 for all participants.

D.4.c.4. BIRTH CONTROL/PREGNANCY ASSESSMENT

Birth Control/ Pregnancy Assessment will be done at baseline/screening at weeks 4, 8, and 12. Any participant who becomes pregnant during participation in the study will be withdrawn. The results will be recorded on a Birth Control/pregnancy Assessment Form.

D.4.c.5. VITAL SIGNS

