Adverse Events (AEs) will be collected using the definition of the UCSF IRB and International Conference on Harmonization (ICH) for Clinical Safety Data Management (ICH-E2A), according to which an adverse event is "any untoward medical occurrence in a patient or clinical investigation participant administered a pharmacological product which does not necessarily have to have a causal relationship with this treatment." An AE can therefore be any unfavorable or unintended sign (including an abnormal laboratory finding), symptom, or disease temporarily associated with the study intervention. This includes any occurrence that is new in onset or aggravated in severity or frequency from the baseline condition, or abnormal results of

diagnostic procedures including laboratory test abnormalities.

E.1.c.3. Serious adverse event definition

Research staff will immediately notify the study physician in the event of a serious adverse event (SAE). In the event of one that is life-threatening or requires hospitalization, the participant's medical status will be monitored and the decision of whether to withdraw the participant from the study will be made on an individual basis by the study physician based on severity and nature of the medical problem. For all adverse reactions that are serious, life-threatening, or require hospitalization, the principal investigator and research coordinator will notify the UCSF IRB and the Federal Drug Administration (FDA) using the standard procedures provided by each agency. An FDA adverse reaction form will be completed at that time.

E.1.d. Participant Withdrawal

Participants will be withdrawn from the study if:

- in the clinical judgment of the investigator, the participant requires acute detoxification from alcohol,
- in the clinical judgment of the investigator, the participant's clinical condition worsens substantially (for example, if weekly alcohol use increases 25% or more over baseline) and it is felt to be in the participant's best interest to obtain alternative treatment including, but not limited to, additional psychotherapy, pharmacotherapy, hospitalization, etc.
- the participant becomes pregnant. Should a participant become pregnant at any time during the study the participant will immediately discontinue study medication. Study medication will not be tapered.

E.2. DATA AND SAFETY MONITORING

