The study will be stopped if, in the judgment of the DSMB or the PI, there are sufficient safety concerns that arise during the conduct of the study that would indicate that participants are being harmed by study interventions. Examples of such safety concerns would be:

- If, after the first 10 participants (33% of the planned enrollment) have completed their study treatment, the interim analysis reveals that more than 50% (i.e. 6 participants) have worsened to a clinically significant degree in the primary outcome measure of alcohol use from baseline to study end.
- Other events that pose unacceptable risks to participants, e.g., multiple SAEs that are judged to be related to study interventions

E.2.h. Rules for Withdrawing Study Participants from the Study Interventions

Participants will be withdrawn from the study if, in the opinion of the DSMB or the PI, there is: sustained clinically significant worsening in the primary outcome measure of alcohol use, unacceptable adverse events judged to be related to study interventions, or any other clinically significant medical, psychiatric, or substance use related poor outcome that makes continued study participation unsafe in the clinical judgment of the PI or DSMB members.

E.2.i. Rules for Breaking the Blind

The blind will be broken for an individual in the study if, in the opinion of the PI or DSMB, there is an emergent clinical need to determine whether a participant is receiving NAC or placebo.

E.3. BENEFITS TO TAKING PART IN THE STUDY

Participants may benefit from the extra physical examination, laboratory tests, and attention to and treatment

PI: [name] of alcohol use disorders. In the informed consent form, participants are instructed: "Taking part in this study may or may not make your health better. If you are in this study, you may benefit from the physical examinations, blood tests, and review of your symptoms. You may respond favorably to the treatment and reduce your drinking and brain injury symptoms, but there is no guarantee that this will happen. Others may benefit from the overall conclusions drawn from the results of this study."

E.4. IMPORTANCE OF THE KNOWLEDGE TO BE GAINED

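### The only numeric example in the stopping rules (E.2.g) counts treatment completers with the arms pooled, so it can understate worsening and cannot tie it to study drug (minor)

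*Combined protocol and SAP*

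**What the plan says.** - **Status of the rule (E.2.g).** "The study will be stopped if, in the judgment of the DSMB or the PI, there are sufficient safety concerns". What follows is a list of examples, not a formal boundary.
- **The numeric example (E.2.g).** Its trigger and threshold are: "first 10 participants (33% of the planned enrollment) have completed their study treatment, the interim analysis reveals that more than 50% (i.e. 6 participants"). The event counted is worsening judged clinically significant, measured "in the primary outcome measure of alcohol use from baseline to study end". No arm is named, and E.2.g gives no cut-off for clinically significant.
- **Withdrawal for worsened drinking.** E.2.h, and E.1.b.6 in nearly the same words, withdraw participants for "sustained clinically significant worsening in the primary outcome measure of alcohol use", in the opinion of the PI or DSMB. E.1.d lets the investigator withdraw a participant whose condition "worsens substantially (for example, if weekly alcohol use increases 25% or more over baseline") when alternative treatment is felt to be in that participant's best interest.
- **Time points.** D.3.g: "Random assignment will be followed by 8 weeks of treatment with NAC or placebo". D.4.b.6 speaks of "completion of the study (as defined by attending Week 12 visit").
- **Allocation (D.3.f).** 1:1 in permuted blocks of unstated size, with participants and investigators blinded.
- **Other safeguards.** The DSMB receives retention data and analyses of the primary outcomes in reports prepared by the PI (E.2.b, E.2.e). The Research Monitor may stop the protocol (E.2.c). A termination form records why a participant left (D.4.b.6).

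**The concern.** The example is meant to flag harm, but two features blunt it.

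First, the denominator is people who completed treatment. Withdrawal for worsened drinking overlaps with the event being counted, and nothing says how a withdrawn participant enters the count. If those who worsen are withdrawn more often than those who do not, the completers look better than the participants as randomised.

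Second, E.2.g asks whether study interventions are harming participants, yet the count pools NAC and placebo. It cannot distinguish harm from study drug from worsening in both arms. It is equally blind to worsening confined to placebo, the direction that E.1.a.6 mentions.

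At stake is the one number offered to those exercising judgment. A reading of not met could reassure when it should not.

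**Working it through.** **1. The plan's own figures.** 10/30 = 33.3%, and the smallest whole number above 50% of 10 is 6. Both reproduce, and 6 confirms a denominator of ten completers.

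**2. Denominator, worked case.** Suppose 12 are randomised and 7 worsen: 7/12 = 58%. Two of the 7 are withdrawn and the other 10 complete. The example then counts 5/10 = 50%, which is not more than 50%, so it is not met.

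**3. Denominator, general.** Let p be the share who worsen, w the fraction of those lost before completing, and v the fraction of the others lost. The share worsened among completers is

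s = p(1 − w) / [p(1 − w) + (1 − p)(1 − v)],

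and the chance of meeting the example is P = Pr(Binomial(10, s) ≥ 6). The documents give no values for p, w or v, so all are assumptions. Rates near 60% are used because the threshold lies there, not because they are expected.

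| p | w | v | s | P |
|---|---|---|---|---|
| 0.60 | 0 | 0 | 0.600 | 0.633 |
| 0.60 | 0.25 | 0 | 0.45/0.85 = 0.529 | 0.451 |
| 0.60 | 0.50 | 0 | 0.30/0.70 = 0.429 | 0.218 |
| 0.60 | 0.25 | 0.25 | 0.600 | 0.633 |
| 0.60 | 0.10 | 0.20 | 0.54/0.86 = 0.628 | 0.701 |
| 0.80 | 0 | 0 | 0.800 | 0.967 |
| 0.80 | 0.25 | 0 | 0.60/0.80 = 0.750 | 0.922 |
| 0.30 | 0 | 0 | 0.300 | 0.047 |
| 0.30 | 0.25 | 0 | 0.225/0.925 = 0.243 | 0.017 |

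The bias needs w greater than v. It vanishes with equal loss and reverses if the others are lost more often. For the same withdrawal (w = 0.25, v = 0), the absolute change is larger at 60% worsening than at 30% or 80%.

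**4. Pooled arms.** Take the first ten completers as 5 NAC and 5 placebo. The 1:1 blocks make this plausible but do not ensure it.

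- 5 v 0 gives 5/10: not met.
- 3 v 3 gives 6/10: met, with no difference between arms.
- With no worsening on placebo, no NAC rate can meet it, because the count cannot exceed 5.

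With X₁ ~ Binomial(5, p₁) for NAC and X₀ ~ Binomial(5, p₀) for placebo, Pr(X₁ + X₀ ≥ 6) is 0.169 at 80% v 10%, 0.501 at 80% v 30%, and 0.377 at 50% in both arms. At 80% v 10%, a split of 4 NAC/6 placebo gives 0.053 and 6/4 gives 0.410.

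**5. What the revised denominator does.** If every worsened participant who leaves is recorded as withdrawn for worsened drinking, and no one is lost for other reasons, the counted share returns to p. At p = 0.60 the chance is again 0.633 whatever w is. In the worked case of step 2, the first 10 randomised include at least 5 of the 7 who worsened. If order is unrelated to worsening, the count reaches 6 or more with probability 1 − (7 × 6)/(12 × 11) = 0.68. The change removes the bias but does not guarantee that the example is met.

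**6. Time point.** The count opens when ten have completed treatment (8 weeks), but worsening runs to study end, and D.4.b.6 ties study completion to week 12. Reading the count once all ten have passed week 12 satisfies both phrases, so this is an ambiguity, not a contradiction.

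**The case against.** The strongest reply is that nothing turns on the example. It sits under a judgment-based stop, so failing to reach 6 of 10 does not bar stopping. A second bullet covers other unacceptable risks, and the DSMB, PI and Research Monitor can each act on other grounds. That stands, and it sets the weight of the point.

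Several stronger readings are tempting, but the documents do not support them.

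- **That withdrawn participants are hidden.** The DSMB sees retention and takes part in E.2.h withdrawals, and the termination form records reasons. Only the count omits them. The omission is also inferred from E.2.g read with the withdrawal sections; no text states it.
- **That withdrawal and the counted event are the same.** E.2.h requires sustained worsening. E.1.d uses weekly alcohol use and adds a best-interest test. They overlap.
- **That the DSMB never sees outcomes by arm.** The primary analyses it receives are defined as between-group (A.1, D.6.a), yet a blinded PI prepares the reports. The documents do not settle it.
- **That interim review is otherwise undescribed.** E.2.b, E.2.e and E.2.f partly cover its content and reporting.
- **That loss can be set at 19%.** The plan does report "with 81% of participants completing the" topiramate pilot, but C.5 defines that as attending week 12 of a 12-week trial, reported at its midpoint. It does not measure loss during 8 weeks of NAC treatment, so no scenario here uses it.

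Pooling also has a defence: it protects the blind in a trial of 30 and covers worsening in either arm. That is a fair reason not to set a by-arm threshold.

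**Conclusion.** The point holds as a minor one. Read literally, the example understates worsening when worsened participants are withdrawn more often than others, and its pooled count cannot show whether study drug is the cause. Two results need no assumed worsening rate: 7 of 12 can read as 5 of 10, and with five per arm 5 v 0 fails while 3 v 3 passes. The probabilities rest on assumed rates and on treating an event without a stated cut-off as well defined. At 60% worsening with a quarter of those withdrawn and no other loss, the chance of meeting the example drops from 0.63 to 0.45; at 80% it drops only from 0.97 to 0.92.

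A reader might infer that the trial could run on through evident harm. The documents do not support that, because stopping rests on judgment and the DSMB has other information. The fault lies in the numeric example, not in safety monitoring as a whole.

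**What to change.** **Main change, E.2.g.** Base the count on the first 10 participants in order of randomisation, once each has completed treatment or been withdrawn. Count withdrawal for worsened drinking as worsened, and show participants lost for other reasons separately. This costs a few words and uses reasons the termination form already records.

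**Optional.** Have the biostatistician who supplies the randomisation list give the DSMB the same count by coded arm, so that the PI stays blinded. The cost is one small table. The downsides are that counts of about 5 per arm are noisy and that the DSMB sees by-arm data. No by-arm threshold is proposed. Applying more than 50% within arms of 5 would mean 3 of 5 in either arm, which raises the chance of a flag from 0.006 (pooled) to 0.112 if 20% worsen in both arms, and from 0.047 to 0.300 if 30% do.

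**Clarification only.** State whether worsening is read at week 8 or week 12, so that treatment completion and study end in E.2.g are reconciled with D.3.g and D.4.b.6. Which time point to use is for the sponsor and DSMB.
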